6.5.7 Clinical Laboratory Adverse Events

The results of all laboratory tests required by the protocol will be recorded in the patient's medical record. All clinically important abnormal laboratory tests occurring during the study will be repeated at appropriate intervals until they return either to baseline or to a level deemed acceptable by the investigator or until a diagnosis that explains them is made.

The criteria for determining whether an abnormal laboratory test result should be reported as an adverse event are as follows:

- 1. Test result is associated with accompanying symptoms, and/or
- 2. Test result requires additional diagnostic testing or medical/surgical intervention, and/or
- 3. Test result leads to a change in study dosing or discontinuation from the study, significant additional concomitant drug treatment or other therapy, and/or
- 4. Test result leads to any of the outcomes included in the definition of a SAE, and/or
- 5. Test result is considered to be an adverse event by the investigator or sponsor.
- *Merely repeating an abnormal test, in the absence of any of the above conditions, does not meet Condition 2 above for reporting as an adverse event.

Any abnormal test result that is determined to be an error does not require reporting as an adverse event, even if it did meet one of the above conditions except for Condition 4.

6.7 Serious Adverse Event (SAE) Reporting

A serious adverse event is – any adverse drug experience occurring at any dose that results in any of the following outcomes:

- Death
- A life-threatening adverse drug experience any adverse experience that places the patient, in the view of the initial reporter, at immediate risk of death from the adverse experience as it occurred. It does not include an adverse experience that, had it occurred in a more severe form, might have caused death.
- Inpatient hospitalization or prolongation of existing hospitalization

- A persistent or significant disability/incapacity a substantial disruption of a person's ability to conduct normal life functions.
- A congenital anomaly/birth defect.

Important medical events that may not result in death, be life-threatening, or require hospitalization may be considered a serious adverse drug experience when, based upon appropriate medical judgment, they may jeopardize the patient or subject and may require medical or surgical intervention to prevent one of the outcomes listed in this definition. Examples of such medical events include allergic bronchospasm requiring intensive treatment in an emergency room or at home, blood dyscrasias or convulsions that do not result in inpatient hospitalization, or the development of drug dependency or drug abuse (21 CFR 312.32).

- Important medical events as defined above, may also be considered serious adverse events. Any important medical event can and should be reported as an SAE if deemed appropriate by the Principal Investigator or the IND Sponsor, Office of Research Education and Regulatory Management (ORERM).
- All events occurring during the conduct of a protocol and meeting the definition of a SAE must by reported to the IRB in accordance with the timeframes and procedures outlined in "University of Texas M. D. Anderson Cancer Center Institutional Review Board Policy on Reporting Serious Adverse Events". Unless stated otherwise in the protocol, all SAEs, expected or unexpected, must be reported to ORERM, regardless of attribution.
- All life-threatening or fatal events, expected or unexpected, and regardless of attribution to the study drug, must have a written report submitted within 24 hours (next working day) of knowledge of the event to the Safety Project Manager in ORERM.
- The MDACC "Internal SAE Report Form for Prompt Reporting" will be used for reporting to ORERM.
- Serious adverse events will be captured from the time the patient signs consent until 30 days after the last dose of drug. Serious adverse events must be followed until clinical recovery is complete and laboratory test have returned to baseline, progression of the event has stabilized, or there has been acceptable resolution of the event.
- Additionally, any serious adverse events that occur after the 30 day time period that are related to the study treatment must be reported to ORERM. This may include the development of a secondary malignancy.

Reporting to FDA:

• Serious adverse events will be forwarded to FDA by the IND Sponsor (Safety Project Manager ORERM) according to 21 CFR 312.32.

It is the responsibility of the PI and the research team to ensure serious adverse events are reported according to the Code of Federal Regulations, Good Clinical Practices, the protocol guidelines, the sponsor's guidelines, and Institutional Review Board policy.

Investigator Communication with Supporting Companies:

The principal investigator has the obligation to report all serious adverse events to the FDA, IRB, and Novartis Pharmaceuticals Integrated Medical Safety. All events reported to the FDA by the investigator are to be filed utilizing the MDACC Serious Adverse Events form.

All events must be reported, by [contact]) along with Novartis SAE Report FAX Cover sheet, to Novartis Pharmaceuticals Integrated Medical Safety Department within 24 hours of learning of it's occurrence. This includes serious, related, labeled (expected) and serious, related, unlabeled (unexpected) adverse experiences. All deaths during treatment or within 30 days following completion of active protocol therapy must be reported within 5 working days.

Any serious adverse event occurring after the patient has provided informed consent and until 4 weeks after the patient has stopped study participation must be reported. This includes the period in which the study protocol interferes with the standard medical treatment given to a patient (e.g. treatment withdrawal during washout period, change in treatment to a fixed dose of concomitant medication).

Serious adverse events occurring more than 4 weeks after study discontinuation need only be reported if a relationship to the Novartis study drug (or therapy) is suspected.

For Comparator Drugs/Secondary Suspects (Concomitant Medications), all serious adverse experiences will be forwarded to the product manufacturer by the investigator.

6.8 Concomitant Medication Assessments

Supportive care medications are permitted with their use following institutional guidelines. For patients who did not undergo orchiectomy, concurrent treatment with LHRH analogue is mandatory and must be recorded.

The concurrent administration of other anticancer therapy, including cytotoxic, hormonal (except LHRH agonists), or immunotherapy is prohibited during study

treatment phase. Use of other investigational drug therapy for any reason is prohibited.

6.9 Removal of Patients from the Study or Study Drug

6.9.1 The investigator must withdraw a patient from study treatment or the study for any of the following reasons:

- Progressive disease. As clinical benefit may be independent of PSAmodulation, progressive disease will not be defined by PSA criteria alone. Rather progressive disease will be defined as any skeletal related event (6.9.2) or tumor progression as defined by RECIST criteria (Appendix I) accompanied by PSA progression or investigator defined clinical progression:
- A serious or intolerable AE occurs as described in 6.7.
- The sponsor or investigator terminates the study.
- The patient requests to be discontinued from the study.

6.9.2 Definition of skeletal-related events (SREs) consisting of the following discrete clinical events or unequivocal radiological changes related to underlying disease progression:

- Progression by radionuclide bone scan with 2 or more new lesions. If progression is noted at the first assessment (ie, Week 12), then a confirmation by a second scan is required 6 or more weeks later that shows a minimum of 2 or more additional new lesions.
- Pathologic bone fracture in the region of cancer involvement that occur spontaneously or as the result of trivial trauma. Each pathologic fracture (vertebral and non-vertebral is to be documented by appropriate diagnostic imaging.
- Radiation therapy to bone radiation administered to bone to palliate painful lesions or prevent or treat pathologic fractures or spinal cord compression.
- Administration of a radioisotope, such as strontium 89, will be included as radiation to bone.
- Cancer-related surgery to bone procedures that are performed to set or stabilize pathologic fractures or areas of spinal cord compression, and surgical procedures that are performed to prevent a pathologic fracture or spinal cord compression.
- Spinal cord or nerve root compression these will be confirmed by MRI. If spinal cord compression occurs in conjunction with vertebral compression, each will be counted seapartely.

6.9.3. Tumor progression as defined by RECIST criteria (see Appendix I).

Bone lesions will not be considered measurable for purposes of RECIST evaluation of disease.

6.10 Other Study Procedures

Supportive care medications are permitted with their use following institutional guidelines. As mentioned in the eligibility criteria, patients must have ongoing gonadal androgen deprivation therapy with LHRH analogues or orchiectomy. Patients, who have not had an orchiectomy, must be maintained on effective LHRH analogue therapy for the duration of the trial.

The concurrent administration of other anticancer therapy, including cytotoxic, hormonal (except LHRH agonists), or immunotherapy is prohibited during study treatment phase. Use of other investigational drug therapy for any reason is prohibited.

7.0 STUDY ACTIVITIES (Appendix J)

On-study tests/visits that must occur within a defined time frame shall have a standing window of allowance that is equal to +/- 2 days for any laboratory testing.

7.1 Screening Period (Days –30 to Day 1)

The following activities/procedures will be conducted during the screening period which may occur within 30 days prior to registration the following baseline evaluations shall be performed:

- Complete medical history must be available in the patient's medical record
- Chest X-ray
- CT or MRI scans of the pelvis and abdomen.
- Bone Scan
- Baseline (pre-treatment) bone marrow biopsy and aspiration within 30 days prior to registration. The specimens will be evaluated by pathology. A portion of bone marrow will be banked for bone marker testing. Patients who have undergone a bone marrow aspirate and biopsy outside the context of this clinical trial are eligible for the trial and may elect not to repeat these baseline studies if the samples were collected within 12 weeks prior to initiation of TKI258 therapy. If a portion of the tissue collected from a previous bone marrow aspirate and biopsy was banked for future use under Lab02-152, Lab03-0320, or another GU clinical trial, the tissue will be requested for this timepoint.
- Electrocardiogram (ECG)
- Echocardiogram or MUGA scan
- 7.2 Screening Period (Days –14 to Day 1)

The following activities/procedures will be conducted during the screening period which may occur within 14 days prior to registration the following baseline evaluations shall be performed:

- Interim medical history including demographics
- Oncology history
- Physical examination
- Vital signs including blood pressure, heart rate, respiratory rate, oral body temperature, weight and height.
- List of concurrent medications and baseline adverse events
- Assessment of ECOG Performance Status
- Laboratory testing:
 - CBC with differential/platelets
 - Serum chemistry must include: BUN, creatinine, total bilirubin, albumin, SGOT [AST], SGPT [ALT], GGT, LDH, amylase, lipase, alkaline phosphatase, fasting glucose, calcium, sodium, magnesium, phosphorus, and potassium
 - PSA assessment.
 - Serum testosterone and DHT levels.
 - Bone Specific Alkaline Phosphatase
 - Blood for Biomarker Studies
 - N-telopeptides in urine

Correlative Studies: Assessment of serum and bone marrow aspirate androgen levels, plus additional serum/plasma banking.

7.3 Treatment Period (Day 1 to Termination of Treatment)

7.3.1 Day 1

Patients who are eligible after screening will be registered and start study treatment after the Screening visit. For all patients, a minimum of 3 sequential ECGs, separated by at least 5-10 minutes, must be performed on cycle 1 day 1 prior to the first administration of TKI258. This is necessary to get an accurate baseline QTc calculation. ECGs will also be performed during the course of treatment (see section 7.4 below)

7.3.2 Day 1 Treatment

At initiation (Day 1) and for the duration of the study, patients will be instructed to take five 100mg capsules by mouth once daily (total of 500 mg of TKI 258 per day). TKI258 should be ingested with sufficient amount of water at least 1 hour prior to a meal (breakfast) or at least 2 hours following a meal (breakfast).

7.4 Evaluation during Treatment

On-study tests/visits that must occur within a defined time frame will have a standing window of allowance that is equal to +/- 3 days for any laboratory testing. If

screening lab tests take place less than 7 days prior to C1D1, laboratory testing will not be repeated.

7.4.1 Beginning on Cycle 1 Day 1 and continuing every 4 weeks thereafter, patients will undergo the following additional testing:

- History and physical exam
- Vital Signs (BP, pulse)
- Weight
- PS (ECOG)
- Assessment of concurrent medications
- Assessment of AEs
- PSA test
- Blood for Biomarker studies (Day 1 of Cycles 2 and 3 only)
- Serum chemistry must include: BUN, creatinine, total bilirubin, albumin, SGOT [AST], SGPT [ALT], GGT, LDH, amylase, lipase, alkaline phosphatase, fasting glucose, calcium, sodium, magnesium, phosphorus, and potassium

7.4.2 On Cycle 1, Days 12 and 26 and Cycle 2 Day 12 patients will undergo the following tests:

- CBC with differential/platelets
- Serum chemistry must include: BUN, creatinine, total bilirubin, albumin, SGOT [AST], SGPT [ALT], GGT, LDH, amylase, lipase, alkaline phosphatase, fasting glucose, calcium, sodium, magnesium, phosphorus, and potassium
- There will be a blood draw for a TKI258 trough concentration (Cycle 2 Day 12 Only) to evaluate the potential relationship of safety and efficacy in regards to steady state drug concentrations.

Note that the Day 26 of Cycle 1 visit could end up being scheduled on the same day as the Day 1 of Cycle 2 visit described above.

7.4.3 Beginning on Cycle 1 Day 1 and every 4 weeks for the first 8 weeks, and every 8 weeks thereafter, patients will undergo the following additional testing:

- Urine N-telopeptide
- Bone Alkaline Phosphatase

7.4.4 ECGs, cardiac enzymes, and MUGA/ECHO during therapy will be assessed as shown below in Table 7.1:

Table	7.1
-------	-----

Assessment	Cycle and Day	Time Point
12-lead ECG	Screening	Anytime
	Cycle 1, Day 1	3 sequential ECGs, separated
		by at least 5 to 10 minute
		intervals pre-dose
	Cycle 1, Day 1	1 ECG six hours post-dose
	Cycle 1, Day 26	1 ECG pre-dose
	Cycle 2, Day 26	1 ECG pre-dose
	Cycle 3, Day 26	1 ECG pre-dose
	Cycle 4+, Day 1	Anytime at the end of the
		previous cycle
	EOT	Anytime
Cardiac enzymes (troponin I	Screening	Anytime to coincide with
or B, CPK, and CPK-MB)		ECHO/MUGA
	Every 12 weeks while	To coincide with
	receiving therapy	ECHO/MUGA
	EOT	Anytime to coincide with
		ECHO/MUGA
ECHO/MUGA	Screening	Anytime to coincide with
		cardiac enzymes
	Every 12 weeks while	To coincide with cardiac
	receiving therapy	enzymes
	ЕОТ	Anytime to coincide with
		cardiac enzymes.

7.4.5 A bone marrow biopsy and aspirate will be performed between 7 and 10 weeks (preferably at week 8) after beginning treatment. The specimens will be evaluated by pathology. A small portion of the bone marrow aspirate will be used for bone marker testing (to include bone marrow androgen levels).

7.4.6 Routine restaging scans and/or other disease assessment diagnostics will be performed every 8 weeks for the first 6 months and every three months thereafter. Such studies can be also be performed at the time of clinical disease progression (at the discretion of the study investigator).

7.5 Final Study Visit:

At the end of the study and within 4 weeks of study drug termination the following will be performed

- History and physical exam
- Vital Signs (BP, pulse)
- Weight

- Eastern Cooperative Oncology Group (ECOG) Performance Status
- Assessment of concurrent medications
- Adverse event evaluation
- Laboratory testing:
- CBC with differential/platelets
- Serum chemistry must include: BUN, creatinine, total bilirubin, albumin, SGOT [AST], SGPT [ALT], GGT, LDH, amylase, lipase, alkaline phosphatase, fasting glucose, calcium, sodium, magnesium, phosphorus, and potassium
- PSA test
- N-telopeptides in urine
- Correlative Studies (serum and bone marrow androgen testing, plus additional serum/plasma banking)
- Disease Status Assessment
- Chest X-ray
- Electrocardiogram (if not done in the past 6 weeks)
- CT or MRI scans of the pelvis and abdomen (if indicated)
- Bone scan (if indicated)
- Bone marrow biopsy and aspirate: The specimens will be evaluated by pathology. A small portion of the bone marrow aspirate will be used for bone marker testing.
- 7.6 Long-Term Follow Up

Patients will be followed a minimum of every 3 months by clinic visit (at M.D. Anderson or a local physician), telephone or e-mail correspondence to assess delayed toxicity and survival time.

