5.0 STUDY TREATMENT(S)

5.1 TKI258 dose and schedule

Patients will receive a single daily oral dose of of TKI258 for 5 consecutive days, followed by a 2-days rest period. Following an initial 4-week cycle at a starting dose of 400 mg 5 days- on and 2 days off, TKI258 may be escalated to 500 mg/day 5 days-on/2 days off if no significant Grade3/4 AEs or laboratory abnormalities are observed. The dose of TKI258 is NOT individually adjusted by weight or body surface area. TKI258 should be ingested with sufficient amount of water at least 1 hour prior to a meal (breakfast) or at least 2 hours following a meal (breakfast). Alternatively, TKI258 may be taken with a. low-fat meal of \leq 500 calories with \leq 20 grams fat.

Treatment cycle

A cycle is arbitrary defined as 28 days (4 weeks) for the purposes of scheduling procedures and evaluations.

A complete treatment cycle is defined as 28 days or 4 weeks.

- TKI258 if given on days 1-5, 8-12, 15-19, 22-26 (5 days on/2 days off) of each cycle.
- The first administration of TKI258 defines Day 1 of the cycle. The last day of a complete cycle is Day 28.

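### Section 7.4 lists on-treatment blood pressure only at the four-weekly Day 1 visits, not at the mid- and late-cycle attendances already planned, so a symptomless rise may wait up to about 28 days

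*Combined protocol and SAP*

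**What the plan says.** Section 7.4.1 sets the recurring visit: "7.4.1 Beginning on Cycle 1 Day 1 and continuing every 4 weeks thereafter, patients will undergo the following additional testing". Its list includes BP and pulse, together with an examination, adverse-event assessment and chemistry.

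Section 7.4.2 adds earlier safety bloods: "7.4.2 On Cycle 1, Days 12 and 26 and Cycle 2 Day 12 patients will undergo the following tests". The list there is blood count, chemistry and, on Cycle 2 Day 12 only, a drug trough level. A note allows one merge: "Note that the Day 26 of Cycle 1 visit could end up being scheduled on the same day" as Day 1 of Cycle 2. Table 7.1 adds single pre-dose ECGs on Day 26 of Cycles 1, 2 and 3 and has no BP row.

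Outside Section 7.4, BP is listed at screening (7.2) and at the final visit (7.5). The schedule section is headed "7.0 STUDY ACTIVITIES (Appendix J)", but that appendix is not in the supplied text.

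Dosing is set in 5.1: "TKI258 if given on days 1-5, 8-12, 15-19, 22-26 (5 days on/2 days off) of each cycle". The two dosing sections differ on the start. Section 5.1 has "Following an initial 4-week cycle at a starting dose of 400 mg 5 days- on and 2 days off", after which "TKI258 may be escalated to 500 mg/day 5 days-on/2 days off if no significant Grade3/4 AEs or laboratory abnormalities are observed". Section 7.3.2 has a "total of 500 mg of TKI 258 per day" from Day 1.

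**The concern.** Table 5-2 acts on hypertension from grade 2: the drug is held, antihypertensive treatment is started or stepped up, and the restart dose depends on whether BP is controlled within 7 days. A rise without symptoms triggers none of this until someone measures it. Exclusion 15e admits patients with BP up to 150/100 mm Hg, with or without medication, so men with treated hypertension can enter.

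The protocol's own safety summary shows that the event occurs with this drug. Table 1-16 reports hypertension in 30 of 200 patients at 500 mg on the same 5 days on/2 days off schedule. Table 1-14 records a grade 4 hypertensive crisis as a Cycle 1 dose-limiting event in study 2107, on this schedule but at 600 mg. A footnote to that table gives a grade 3 hypertension on Cycle 2 Day 8 in study 2101, at 100 mg on a different schedule. The two severe cases are single events and give no rate. They do show that severe hypertension has arisen in Cycle 1 and between Day 1 visits.

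What is at stake is the delay before a required hold and treatment, at a time when patients already attend for bloods or an ECG.

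**Working it through.** The plan states no figure to reproduce, so the check is calendar arithmetic.

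**Inputs.** Dosing days come from 5.1, BP days from 7.4.1, other attendances from 7.4.2 and Table 7.1, and event counts from Tables 1-16 and 1-17.

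**1. Gaps as listed.** BP falls on study Days 1, 29, 57 and 85. Each gap is 28 days (29 − 1, 57 − 29, 85 − 57). Doses per cycle are 4 × 5 = 20, so 20 doses fall between successive listed readings.

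**2. Attendances without a listed BP.**

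| Attendance | Study day | Dosing day? | Days to next listed BP |
|---|---|---|---|
| Cycle 1 Day 12 | 12 | yes | 29 − 12 = 17 |
| Cycle 1 Day 26 | 26 | yes | 29 − 26 = 3 |
| Cycle 2 Day 12 | 28 + 12 = 40 | yes | 57 − 40 = 17 |
| Cycle 2 Day 26 | 28 + 26 = 54 | yes | 57 − 54 = 3 |
| Cycle 3 Day 26 | 56 + 26 = 82 | yes | 85 − 82 = 3 |

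**3. Gaps with BP added at all five, on nominal days and before the dose.** Readings fall on Days 1, 12, 26, 29, 40, 54, 57, 82 and 85.

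| Cycle | Gaps (days) | Doses in each gap | Longest gap |
|---|---|---|---|
| 1 | 11, 14, 3 | 9, 10, 1 | 14 |
| 2 | 11, 14, 3 | 9, 10, 1 | 14 |
| 3 | 25, 3 | 19, 1 | 25 |
| 4 onward | 28 | 20 | 28 (unchanged) |

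**4. Mean wait.** Assume a sustained rise whose onset is spread evenly over the 28 days. The mean wait to the next reading is the sum of squared gaps divided by (2 × 28).
- As listed: 28² / 56 = 784 / 56 = 14.0 days.
- Cycles 1 and 2 with the change: (121 + 196 + 9) / 56 = 326 / 56 = 5.8 days.
- Cycle 3 with the change: (625 + 9) / 56 = 634 / 56 = 11.3 days.

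The documents give no onset data, so these means are illustrative. The longest gaps do not depend on that assumption.

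**5. If Cycle 1 Day 26 is merged with Cycle 2 Day 1.** Merged on Day 29, the added readings give Cycle 1 gaps of 11 and 29 − 12 = 17 days, and a mean wait of (121 + 289) / 56 = 7.3 days. Merged on Day 26, a BP is already listed that day, and the first gap under the present text is 26 − 1 = 25 days.

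**6. Visit windows.** Section 7.4 allows ± 3 days for laboratory tests. If that also applies to visits, the present gap can reach 28 + 3 = 31 days (one late visit) or 28 + 6 = 34 days (one early, the next late). A Day 12 draw could fall on Days 9 to 15, which include rest Days 13 and 14.

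**7. Which doses are affected.** Under 7.3.2 the first 20 doses at 500 mg are in Cycle 1. Under 5.1, for a patient escalated at the start of Cycle 2, they are in Cycle 2. Either way they lie between two Day 1 readings.

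**8. Event rates (any grade, any cause, any onset; exact 95% intervals).** At 500 mg in the global studies: 30/200 = 15.0% (10.4 to 20.7). At 400 mg in Japanese study 1101: 4/9 = 44.4% (13.7 to 78.8), a small and different population. If the 15.0% carried over, 40 × 0.15 = 6 patients would have hypertension of some grade. No rate is given for Cycle 1 onset or for grade 2 and above, so the number whose hold would come earlier cannot be derived.

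**The case against.** The case for leaving the plan alone is reasonable. Section 7.4 is a minimum, and investigators may measure BP at any contact. Section 1.7.1 describes the common adverse events as reversible and mostly grade 1 or 2. At 500 mg in study 2107 the only Cycle 1 dose-limiting event among 15 patients was a grade 2 sinus bradycardia; the hypertensive crisis was at a dose not used here. Appendix J may already list the readings. The change does little in Cycle 3 and nothing from Cycle 4. These points stand and limit the weight of the finding. They do not remove it, because the section as written does not assure a reading between Day 1 visits, and early cycles are where the change shortens the gap most.

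Four stronger readings are tempting, and the documents do not support them.

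- **No BP on any dosing day with bloods or an ECG.** Day 1 of every cycle is a dosing day with chemistry and BP, and Cycle 1 Day 1 also has ECGs. The gap concerns the later attendances in the cycle.
- **Escalation under 5.1 without a relevant BP.** A BP, examination and adverse-event assessment are listed at Cycle 2 Day 1, which is when that decision falls.
- **The two rest days before each Day 1 hide a rise.** Nothing in the documents shows that BP falls over two rest days. A sustained rise, as assumed in the mean-wait figures, would still be present on Day 29.
- **Serious harm is likely.** No relevant event rate is given.

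**Conclusion.** The concern holds for Section 7.4 as worded. BP after Cycle 1 Day 1 is listed only every four weeks, and five other planned attendances on nominal dosing days carry none, apart from a possible merge of the Cycle 1 Day 26 visit. The consequence is delay: up to about 28 days before a rise that Table 5-2 would act on is sure to be measured. It arises whichever starting dose governs.

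The size rests on nominal visit days, on no unscheduled readings being taken, and on Appendix J not listing more. The effect on patients cannot be quantified. No stated rule is broken, so this is a worthwhile, low-cost improvement to a design choice.

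**What to change.** Add a BP reading to the Cycle 1 Day 12, Cycle 1 Day 26 and Cycle 2 Day 12 attendances in 7.4.2, and to the Cycle 2 and Cycle 3 Day 26 pre-dose ECGs in Table 7.1.

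- Take it on a dosing day where the visit window allows, without narrowing the laboratory window.
- If blood is drawn away from the site, accept a local cuff reading reported to the site.
- If Cycle 1 Day 26 and Cycle 2 Day 1 are merged, the single BP at that visit is enough; require no extra attendance.
- Align Appendix J if it differs. Table 5-2 needs no change.

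The cost is a few minutes per attendance, assuming staff are present at the draw or ECG, plus the schedule wording. Slightly more low-grade hypertension will be recorded, and some patients will have a dose held earlier. If closer monitoring is wanted from Cycle 4 on, it would need a separate decision, since this change does not reach those cycles.
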